#### Confidentiality Statement

Data and information contained in this document are considered to constitute trade secrets and confidential commercial information, and the legal protections provided to such trade secrets and confidential information are hereby claimed under the provisions of applicable law. No part of this document may be publicly disclosed without the written consent of Philip Morris Products S.A.

- P3P 2 vs P3P 3, to describe the effect of an increase of nicotine powder concentration from 2.5% to 5%
- P3P 2 vs P3P 4, to describe the effect of a decrease from 2.25  $\mu\text{m}$  to 1.8  $\mu\text{m}$  of the median particle size in the nicotine powder
- P3P 2 vs P3P 1, to describe the effect of flavor

The values of  $\text{AUC}_{\text{VAS fix (0-4h)}}$  will be summarized by P3P variant (Table 15.2.4.3) and listed (Listing 15.3.4.2). Boxplot of  $\text{AUC}_{\text{VAS fix (0-4h)}}$  by P3P variant will be presented (Figure 15.1.4.3).

A mixed model will be conducted for the values of  $\text{AUC}_{\text{VAS fix (0-4h)}}$  for fixed puffing regimen with fixed terms for sequence, product variant and two dummy variables for Day 3 and Day 4 (i.e two variables taking value 1 for Day 3 and Day 4 respectively and value 0 for the other study days) and using subject nested within sequence as random effect. In this way Day 1 and Day 2 will be combined to address the multicollinearity as planned in the protocol. The SAS code to be used is shown below:

```
proc mixed data=_data_;  
  class Sequence Product_Variant Day3 Day4 Subject;  
  model AUCVAS fix (0-4h) = Sequence Product_Variant Day3 Day4 / ddfm=SAT s;  
  random Subject(Sequence) / sub=Subject type=CSH;  
  lsmeans Product_Variant / cl diff alpha=0.05;  
run;
```

In case of model convergence issues, this will be reported in the study report and the variance component (type=VC) covariance structure will be investigated.

Least square means and differences will be presented for the analysis of  $\text{AUC}_{\text{VAS fix (0-4h)}}$  together with 95% confidence interval for the following effects of interest (Table 15.2.4.4):

- P3P 2 vs P3P 3, to describe the effect of an increase of nicotine powder concentration from 2.5% to 5%
- P3P 2 vs P3P 4, to describe the effect of a decrease from 2.25  $\mu\text{m}$  to 1.8  $\mu\text{m}$  of the median particle size in the nicotine powder
- P3P 2 vs P3P 1, to describe the effect of flavor

The values of VAS for Craving and changes from baseline for *ad libitum* use will be summarized by P3P variant and time point (Table 15.2.4.5) and listed (Listing 15.3.4.3). Individual profiles and profiles of the raw means will be produced by P3P variant and time point (Figures 15.1.4.4 and 15.1.4.5).

The same mixed model as for fixed puffing regimen will be conducted for the values of VAS for Craving for *ad libitum* use. Least square means and differences will be presented for the analysis of the values of VAS for Craving for *ad libitum* use together with 95% confidence interval for the same effects of interest of VAS for Craving for fixed puffing regimen (Table 15.2.4.6).

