12.6.2.1 PK parameters for *ad libitum* use

PK parameters for *ad libitum* use will be summarized by P3P variant and analyzed using a mixed model with fixed terms for sequence, study day, product variant, and using subject nested within sequence as random effect. Nicotine PK profiles will be summarized and plotted over time by P3P variant.

Confidentiality Statement

Data and information contained in this document are considered to constitute trade secrets and confidential commercial information, and the legal protections provided to such trade secrets and confidential information are hereby claimed under the provisions of applicable law. No part of this document may be publicly disclosed without the written consent of Philip Morris Products S.A.

Details of model term categories for product variant and study day, accounting for multicollinearity between Day 1 and P3P 3 use, will be provided in the SAP.

12.6.2.2 **VAS Craving Assessments**

VAS craving assessments and AUC_{VAS} scores will be summarized over time by P3P variant and by regimen. The VAS scores will be assessed using a mixed model with sequence, study day, product variant, baseline value prior to product use, and the interaction of product and time point as fixed effects and subjects as random effect including the assessment time points as repeated measurements. AUC_{VAS} scores will be analyzed using the same model as for the PK parameters, including adjustment of baseline VAS value.

Details of model term categories for product variant and study day, accounting for multicollinearity between Day 1 and P3P 3 use, will be provided in the SAP.

12.6.2.3 **Questionnaires (Adapted mCEQ and SQ)**

Adapted mCEQ subscale scores and SQ answers will be summarized with descriptive statistics and displayed graphically by P3P variant. The scores/answers will be analyzed using a mixed model with fixed terms for sequence, study day, product variant, and using subject nested within sequence as a random effect.

Details of model term categories for product variant and study day, accounting for multicollinearity between Day 1 and P3P 3 use, will be provided in the SAP.

12.6.2.4 **Puffing Topography**

HPT parameters will be summarized by P3P variant and by product use regimen with arithmetic means, arithmetic CV, and 95% CIs.

12.6.3 **Safety Endpoints**

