#### Confidentiality Statement

Data and information contained in this document are considered to constitute trade secrets and confidential commercial information, and the legal protections provided to such trade secrets and confidential information are hereby claimed under the provisions of applicable law. No part of this document may be publicly disclosed without the written consent of Philip Morris Products S.A.

Version	Date of Revision	Revision
Draft version 1.1	25APR2018	
[REDACTED] updated sections 7.1.2.3, 12.6.2.2.1, 13.1.3.1, 13.1.4 and 16.2 (Table 21) and the numbering of figures 15.1.4 as agreed with [REDACTED] and [REDACTED]
 
[REDACTED]
 
The update occurred prior to database lock but after the review of the draft results of the PK interim analysis
 
In section 7.1.2.3 it was clarified that the considerations regarding the period of estimation, the number of data points included into the calculation and the goodness of fit for apparent terminal elimination half-life can be applied only in case of non-compartmental analysis
 
In section 12.6.2.2.1 were added the new individual VAS craving result-time profiles
 
In section 13.1.3.1 it was clarified how to manage for the calculation of the PK parameters the background-corrected values that are below the bioanalytical LOQ threshold
 
In section 13.1.4 it was clarified which are the model-based estimated PK parameters whose geometric mean and CV% have to be presented
 
In section 16.2 (Table 21) and wherever applicable the numbering of figures was updated due to the insertion of the new individual VAS craving result-time profiles

Final version 2.0	30APR2018	[REDACTED] issued the final version 2.0 after Sponsor's approval

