## 4.1 Definitions for Statistical Analysis

The following special terms are used in this SAP:

Baseline	For PK/PD analysis and VAS-craving assessment, baseline is defined as the last assessment prior to time point of start of product use at the fixed puffing regimen ( $T_0 \text{ fix}$ ) for fixed puffing regimen and as the last assessment prior to time point of start of first product use at the ad libitum use period ( $T_0 \text{ ad lib}$ ) for ad libitum use, for each study day of exposure. For all the other endpoints, the baseline is defined as the last available assessment prior to $T_0 \text{ fix}$ on Day 1, except for vital signs, where baseline is defined as the last assessment prior to $T_0 \text{ fix}$ for each study day of exposure.
Safety follow-up	After discharge on Day 5 or after discontinuation, a 7-day safety follow-up will be done
End of Study	The end of the study (EOS) for a subject is defined as either the Discharge at Day 5, or the date of early termination of the subject, plus the 7 days for the Safety Follow-up Period. The end of the whole study corresponds to the individual EOS of the last subject.
Enrollment	On Admission Visit for eligible subjects after all applicable inclusion and exclusion criteria have been satisfactorily assessed and met.
Randomization	Assignment to the respective sequence of product use at Day 2.
Screen failure	Subject who signs the ICF but is not enrolled.

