#### Confidentiality Statement

Data and information contained in this document are considered to constitute trade secrets and confidential commercial information, and the legal protections provided to such trade secrets and confidential information are hereby claimed under the provisions of applicable law. No part of this document may be publicly disclosed without the written consent of Philip Morris Products S.A.

The actual VAS assessments times post-exposure collected in the CRF will be used in the computation of the AUCVAS, with the exception of pre-exposure assessment time which will be considered as time zero ( $T_0$  fix or  $T_0$  ad lib).

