## Protocol P3P-PK-01-CH

## Statistical Analysis Plan

Final v2.0 / 30 Apr 2018

Confidential

Page 38 of 90

we are expecting a low drop-out rate, 3 subjects will be allocated to each sequence. Therefore, 18 subjects will be randomized.

A sufficient number of eligible subjects will be enrolled and exposed to P3P 3 at Admission (Day -1) and Day 1 to ensure randomization of 18 subjects to one of six possible sequences at Day 2.

A sensitivity analysis was added in Section 12.6.1 "Primary Analyses" to evaluate the impact of including the Study Day in the analysis of specific PK parameters.

The definitions of enrolled population and randomized population were added

No shift table for ECG data will be provided.

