## 12.6.2.2 Questionnaires

### 12.6.2.2.1 Visual Analogue Scale for Craving

The values of VAS for Craving and changes from baseline for fixed puffing regimen will be summarized by P3P variant and time point (Table 15.2.4.1) and listed (Listing 15.3.4.1). Individual profiles and profiles of the raw means will be produced by P3P variant and time point (Figures 15.1.4.1, 15.1.4.2).

A mixed model will be conducted for the values of VAS for Craving for fixed puffing regimen with fixed terms for sequence, product variant, two dummy variables for Day 3 and Day 4 (i.e two variables taking value 1 for Day 3 and Day 4 respectively and value 0 for the other study days), baseline value prior to product use, the time point and the interaction of product variant and time point and using subject nested within sequence as a random effect including the assessment timepoints as repeated measurements. In this way Day 1 and Day 2 will be combined to address the multicollinearity as planned in the protocol. The SAS code to be used is shown below:

```
proc mixed data=_data_;  
  class Sequence Product_Variant Day3 Day4 Time_Point Subject;  
  model VAS = Sequence Product_Variant Day3 Day4 VAS_Baseline  
  Product_Variant*Time_Point / ddifm=SAT s;  
  repeated Time_Point / subject=Subject type=CSH;  
  random Subject(Sequence) / sub=Subject type=CSH;  
  lsmeans Product_Variant / cl diff alpha=0.05;  
  lsmeans Product_Variant*Time_Point / slice=Time_Point alpha=0.05 diff cl;  
run;
```

In case of model convergence issues, this will be reported in the study report and the variance component (type=VC) covariance structure will be investigated.

Least square means and differences will be presented for the analysis of the values of VAS for Craving together with 95% confidence interval for the following effects of interest (Table 15.2.4.2):

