#### Confidentiality Statement

Data and information contained in this document are considered to constitute trade secrets and confidential commercial information, and the legal protections provided to such trade secrets and confidential information are hereby claimed under the provisions of applicable law. No part of this document may be publicly disclosed without the written consent of Philip Morris Products S.A.

The values of  $AUC_{VAS}$  ad libitum (0-4h) will be summarized by P3P variant (Table 15.2.4.7) and listed (Listing 15.3.4.4). Boxplot of  $AUC_{VAS}$  ad libitum (0-4h) by P3P variant will be presented (Figure 15.1.4.6).

The same mixed model as for fixed puffing regimen will be conducted for the values of  $AUC_{VAS}$  ad libitum (0-4h) for *ad libitum* use. Least square means and differences will be presented for the analysis of  $AUC_{VAS}$  ad libitum (0-4h) together with 95% confidence interval for the same effects of interest of  $AUC_{VAS}$  fix (0-4h) for fixed puffing regimen (Table 15.2.4.8).

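### The SAP's AUC_VAS craving model omits the baseline VAS adjustment that Protocol 12.6.2.2 specifies, although its time-point craving model keeps it

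*SAP*

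**What the plan says.** Protocol 12.6.2.2 sets out two craving analyses. Scores by time point are modelled with the pre-use value as a fixed effect. AUC_VAS takes the PK-parameter model, "including adjustment of baseline VAS value".

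SAP 12.6.2.2.1 keeps baseline in the first analysis: "model VAS = Sequence Product_Variant Day3 Day4 VAS_Baseline", and its prose agrees. For AUC_VAS under fixed puffing, the prose lists sequence, product variant and indicators for Days 3 and 4, and the code is "model AUCVAS fix (0-4h) = Sequence Product_Variant Day3 Day4 / ddfm=SAT s". For ad libitum use the SAP says "The same mixed model as for fixed puffing regimen will be conducted for the values of" AUC_VAS, so the omission carries over.

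The covariate exists. SAP 4.1 states "For PK/PD analysis and VAS-craving assessment, baseline is defined as the last assessment prior to time point of start of product use", separately for each regimen and each study day.

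Two protocol passages are less specific. The synopsis gives AUC_VAS the PK model on the original scale and does not mention baseline. Section 12.6.2 applies the general PK approach to PD endpoints.

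The SAP revision history records only one change to this section: "In section 12.6.2.2.1 were added the new individual VAS craving result-time profiles". The visible part of the SAP's list of changes from the protocol opens with "A sensitivity analysis was added in Section 12.6.1", then covers population definitions and the dropped ECG shift table. It does not mention AUC_VAS, but text before that list is missing from the public copy.

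**The concern.** Two analyses of the same craving scores are adjusted differently, and one of them is not the analysis the protocol specifies.

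The design makes this matter for one contrast. P3P 1, 2 and 4 are randomised over Days 2 to 4, so differences in pre-use craving balance out on average. P3P 3 is not randomised: everyone uses it on Day 1. The model then treats Days 1 and 2 as one level so that P3P 3 can be estimated at all. Any Day 1 versus Day 2 difference in craving before use is therefore absorbed by the P3P 3 coefficient, and hence by P3P 2 vs P3P 3, the contrast meant to describe nicotine concentration. A baseline covariate is the only term that could take up part of such a difference.

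**Working it through.** **1. The texts side by side**

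| Analysis | Protocol 12.6.2.2 | SAP prose | SAP code |
|---|---|---|---|
| Craving by time point | baseline included | baseline included | `VAS_Baseline` present |
| AUC_VAS, fixed | PK model plus baseline | no baseline | no baseline |
| AUC_VAS, ad libitum | PK model plus baseline | same model as fixed | none separate |

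**2. Does AUC_VAS adjust itself?** SAP 7.3.1 puts the pre-use score in the trapezoid, "with the exception of pre-exposure assessment time which will be considered as time zero". Its weight is half the first interval over 240 minutes: (4/2)/240 = 0.8% for fixed puffing and (10/2)/240 = 2.1% for ad libitum use. So it does not. This is also the only link between baseline and AUC_VAS that the documents guarantee.

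**3. Where a Day 1 difference goes.** Let b1 and b2 be mean pre-use VAS on Days 1 and 2, and β the within-subject slope of time-averaged AUC_VAS on baseline. Days 3 and 4 have their own terms, so

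bias in (P3P 2 − P3P 3) = β × (b2 − b1).

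Take β = 0.5 and Day 1 one point higher (both assumed): 0.5 × (−1) = −0.50. The planned layout was simulated with 6 sequences × 3 = 18 subjects, 72 records, subject as a fixed effect and 4,000 runs:

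| Contrast | Without baseline: mean (SD) | With baseline: mean (SD) |
|---|---|---|
| P3P 2 vs P3P 3 | −0.50 (0.39) | −0.01 (0.36) |
| P3P 2 vs P3P 4 | −0.01 (0.34) | −0.01 (0.30) |

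For assumed slopes of 0.3 to 0.8 and differences of 0.5 to 2 points, the shift runs from 0.3 × 0.5 = 0.15 to 0.8 × 2 = 1.6 points on the 0–10 scale.

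**4. Precision.** With within-subject correlation r, omitting baseline inflates the standard error by 1/√(1 − r²) − 1: 4.8%, 15.5% and 40.0% at r = 0.3, 0.5 and 0.7. The term is estimable: with subject fixed, design rank goes from 23 to 24, and residual degrees of freedom from 72 − 23 = 49 to 48.

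**5. Form of the term when subject is random.** One raw baseline term mixes between- and within-subject slopes. The alternative is to split it into the subject's mean and the session's deviation from it. Both were simulated in a random-intercept REML model, 2,000 runs per setting. Assumptions: Day 1 lower by one within-subject SD, baseline SDs 2 between and 1 within, between-subject slope 0.9, baseline error-free, no true product effect. Bias in P3P 2 − P3P 3, with 95% interval coverage:

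| Within-subject slope r | No baseline | One raw term | Split |
|---|---|---|---|
| 0 | 0.01 (96%) | −0.22 (92%) | ≤ 0.02 in size |
| 0.3 | 0.28 (89%) | −0.21 (91%) | ≤ 0.02 in size |
| 0.5 | 0.49 (75%) | −0.13 (93%) | ≤ 0.02 in size |
| 0.7 | 0.71 (57%) | −0.06 (95%) | ≤ 0.02 in size |

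Coverage for the split is 95–96% throughout. With equal between- and within-subject slopes, the raw and split forms agree.

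The ranking changes if the single self-rating is noisy. With within-subject reliability λ, the split slope shrinks to λr and leaves a bias of r(1 − λ) per SD of shift: 0.5 × 0.3 = 0.15 at r = 0.5, λ = 0.7, and 0.7 × 0.5 = 0.35 at r = 0.7, λ = 0.5. Simulation over r = 0.5 to 0.7 and λ = 0.5 to 0.7 gave 0.14 to 0.36 for the split and −0.03 to 0.18 for the raw term. With no Day 1 shift, no form is biased.

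**The case against.** The strongest reply is that the protocol is not of one mind. Within one bullet, the synopsis names baseline for the time-point model and then gives AUC_VAS the PK model, which has none. Section 12.6.2 also sends PD endpoints to the PK approach, and section 12.1 leaves full detail to the SAP. On that view the SAP followed the synopsis. This stands only in part: silence in a summary does not cancel the explicit instruction in the section written for this endpoint, and it does not explain why the two SAP craving models differ.

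The harm is also hypothetical, and this stands. No Day 1 shift and no slope are documented. Each session follows at least 10 hours without nicotine, and subjects have already tried P3P 3 at Admission. The SAP states no hypothesis, makes no claim from individual intervals, and sets no reporting flag on the AUC_VAS analysis tables in its Table 21. The time-point model already supplies a baseline-adjusted comparison.

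A reader might infer from the error-free simulation that one raw baseline term is wrong and the split must be required. The documents do not support that. Neither mentions a split, and the SAP's own craving model uses the raw term. Which form is less biased depends on slopes and a reliability that nobody has stated. Splitting only the AUC_VAS models would also leave the two craving analyses adjusted differently. Finally, the simulations use a plain random intercept rather than the SAP's first-choice CSH structure, so the coverage figures are illustrative.

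**Conclusion.** The discrepancy is confirmed: the protocol specifies baseline adjustment for AUC_VAS, and the SAP leaves it out in prose and code for both regimens. It should be corrected or declared.

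The consequence is modest. P3P 2 vs P3P 3 is exposed to bias of β times any Day 1 versus Day 2 difference in pre-use craving; every figure for that bias rests on assumed values. P3P 2 vs P3P 1 and P3P 2 vs P3P 4 are exposed only to loss of precision.

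Two stronger conclusions are tempting. One is that the change was made without being declared. With part of the SAP missing from the public copy, that cannot be determined. The other is that the planned P3P 2 vs P3P 3 estimate is biased. The documents show only that it is unprotected against one possible imbalance. Adjustment would not remove the wider confounding of P3P 3 with Day 1.

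**What to change.** Add the session's pre-use VAS to the AUC_VAS model in prose and code: put `VAS_Baseline` after `Day4` in the model statement, for fixed puffing (Table 15.2.4.4) and ad libitum use (Table 15.2.4.8). This matches Protocol 12.6.2.2 and the time-point model.

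For ad libitum use, show the unadjusted result beside the adjusted one. That baseline is taken after the same variant was used the same morning, so adjusting may remove part of the product effect.

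Optionally, add a sensitivity analysis that splits baseline into subject mean and session deviation, or fits subject as fixed. It would show whether mixing the two slopes matters in these data.

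If the omission is deliberate, state it and the reason among the changes from the protocol.

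The data are already collected. The cost is one covariate, one degree of freedom (two if split) and one extra table. If the within-subject slope is near zero, intervals widen slightly. For the split form at r = 0, the mean half-width for P3P 2 vs P3P 3 goes from 0.770 to 0.780 (about 1%) with no Day 1 shift, and from 0.772 to 0.830 (about 7.5%) with a one-SD shift.

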#### Confidentiality Statement

Data and information contained in this document are considered to constitute trade secrets and confidential commercial information, and the legal protections provided to such trade secrets and confidential information are hereby claimed under the provisions of applicable law. No part of this document may be publicly disclosed without the written consent of Philip Morris Products S.A.

The values of  $AUC_{VAS}$  ad libitum (0-4h) will be summarized by P3P variant (Table 15.2.4.7) and listed (Listing 15.3.4.4). Boxplot of  $AUC_{VAS}$  ad libitum (0-4h) by P3P variant will be presented (Figure 15.1.4.6).

The same mixed model as for fixed puffing regimen will be conducted for the values of  $AUC_{VAS}$  ad libitum (0-4h) for *ad libitum* use. Least square means and differences will be presented for the analysis of  $AUC_{VAS}$  ad libitum (0-4h) together with 95% confidence interval for the same effects of interest of  $AUC_{VAS}$  fix (0-4h) for fixed puffing regimen (Table 15.2.4.8).

### **12.6.2.2.2 Adapted Modified Cigarette Evaluation Questionnaire**

The adapted mCEQ subscale scores will be summarized by P3P variant (Table 15.2.4.9). The answers to the individual questions along with the scores will also be listed (Listing 15.3.4.5). Boxplot of adapted mCEQ subscale scores by P3P variant will be presented (Figure 15.1.4.7).

A mixed model will be conducted for the adapted mCEQ subscale scores with fixed terms for sequence, product variant and two dummy variables for Day 3 and Day 4 (i.e two variables taking value 1 for Day 3 and Day 4 respectively and value 0 for the other study days) and using subject nested within sequence as random effect. In this way Day 1 and Day 2 will be combined to address the multicollinearity as planned in the protocol. The SAS code to be used is shown below:

```
proc mixed data=_data_;  
  class Sequence Product_Variant Day3 Day4 Subject;  
  model mCEQ_Subscale_Score = Sequence Product_Variant Day3 Day4 / ddfm=SAT s;  
  random Subject(Sequence) / sub=Subject type=CSH;  
  lsmeans Product_Variant / cl diff alpha=0.05;  
run;
```

In case of model convergence issues, this will be reported in the study report and the variance component (type=VC) covariance structure will be investigated.

Least square means and differences will be presented for the analysis of the adapted mCEQ subscale scores together with 95% confidence interval for the following effects of interest (Table 15.2.4.10):

- P3P 2 vs P3P 3, to describe the effect of an increase of nicotine powder concentration from 2.5% to 5%
- P3P 2 vs P3P 4, to describe the effect of a decrease from 2.25  $\mu$ m to 1.8  $\mu$ m of the median particle size in the nicotine powder
- P3P 2 vs P3P 1, to describe the effect of flavor

